## 1.2. Background on Study Intervention(s)

A list of study interventions and their marketing authorization status is provided in Appendix 11.2.

### 1.2.1. Obeldesivir

#### 1.2.1.1. General Information

Obeldesivir is a mono-5'-isobutyryl ester prodrug of GS-441524, and following oral administration, is extensively hydrolyzed presystemically to yield the parent nucleoside of RDV, GS-441524. The prodrug ODV was designed to specifically increase the oral bioavailability of GS-441524.

For further information on ODV, refer to the current investigator's brochure (IB).

#### 1.2.1.2. Relevant Nonclinical Data

For further information on ODV, refer to the current IB.

#### 1.2.1.3. Clinical Studies of ODV

Obeldesivir has been evaluated in the COVID-19 clinical development program. Early and late phase studies in the ODV COVID-19 program characterized the pharmacokinetics (PK) profile and evaluated the DDI potential of ODV. Obeldesivir was safe and well tolerated at single doses of 100 mg to 1600 mg and multiple doses of 500 mg twice daily and 900 mg once daily for CCI. In 2 Phase 3 studies, ODV CCI, and it was found to be safe and well tolerated in adults and adolescents with COVID-19 (approximately 2400). In a Phase 2 study, ODV CCI was found to be safe and well tolerated in 3 pediatric participants ( $\geq 6$  to  $< 18$  years of age) with COVID-19.

For further information on ODV refer to the current IB.

### 1.2.2. Information About Auxillary Medicinal Products/Noninvestigational Medicinal Products

Auxiliary medicinal products/noninvestigational medicinal products are not used in this study.

## 1.3. Rationale for This Study

Respiratory syncytial virus is a well-recognized cause of respiratory tract illness worldwide {World Health Organization (WHO) 2024}. There are currently no approved oral agents for the treatment of RSV infection, and there remains a significant unmet need for safe and effective oral treatments for the pediatric population {Borchers 2013, Oey 2023, Rocca 2021}.

Obeldesivir is an ester prodrug of the parent nucleoside of RDV, GS-441524. It has potent in vitro antiviral activity against RSV and exhibits therapeutic efficacy against RSV in an African green monkey animal model. Following oral administration, ODV delivers high systemic exposures of GS-441524 and adequate formation of the active nucleoside triphosphate metabolite, GS-443902, in tissues where RSV replicates. Administration of oral ODV therefore represents a promising approach for the treatment of RSV.

This study will evaluate ODV compared with placebo in nonhospitalized pediatric participants from birth to < 5 years of age with RSV infection for whom there are no existing oral therapies that are authorized or approved. Patients at high risk of severe RSV disease may benefit from effective antiviral therapy that could result in symptom improvement, a shorter duration of illness, reduced progression to severe disease, and reduced incidence of medically attended visits (MAVs) or hospitalizations.

#### 1.4. Rationale for Dose Selection of Study Drug

The PK and safety of ODV were evaluated in a comprehensive clinical program with 6 Phase 1 studies in healthy adult participants (first-in-human Study GS-US-611-6248, absorption, distribution, metabolism, and excretion Study GS-US-611-6408, DDI Studies GS-US-611-6409 and GS-US-611-6469, Japanese bridging Study GS-US-611-6586, and renal impairment Study GS-US-611-6472 [interim data]) and 2 pivotal Phase 3 studies in adult and adolescent participants with COVID-19 (Studies GS-US-611-6549 and GS-US-611-6273). Obeldesivir was generally safe and well tolerated (most adverse events [AEs] were Grade 1 in severity) following single doses up to 1600 mg and multiple doses of CCI, 500 mg twice daily, and 900 mg once daily for CCI in healthy participants and CCI in participants with COVID-19.

A preliminary GS-441524 population PK (PopPK) model incorporating weight-based allometric scaling on clearance and volume parameters was developed using nonlinear mixed-effects modeling and data obtained from the above-listed studies (except Study GS-US-611-6408). The developed PopPK model was used to evaluate intrinsic and extrinsic factors impacting the ODV PK. Body weight, estimated glomerular filtration rate (eGFR), and presence of COVID-19 disease were found to have a significant impact on the PK of GS-441524. The preliminary model was also used to facilitate the initial development of the age-appropriate pediatric CCI formulation. This model was updated with the PK data obtained from the relative bioavailability study of ODV (GS-US-611-6468) that evaluated the pediatric CCI formulation relative to the ODV tablet and from data obtained from 3 pediatric participants from the Phase 2/3 pediatric study of ODV in treatment of COVID-19 (GS-US-611-6464).

After incorporating an age-based renal maturation function in the pediatric PopPK model, exposures were extrapolated to pediatrics to select ODV doses to be evaluated in RSV pediatric participants < 5 years of age. Virtual pediatric subpopulations were used for the dose projection simulations, based on information from 3 public databases: World Health Organization (WHO), National Health and Nutrition Examination Survey (NHANES), and Fenton Preterm Growth Calculations.

For each age-weight group, ODV doses were selected to match predicted GS-441524 exposures associated with the Phase 2 adult dosing regimen (Study GS-US-685-6819). CCI

CCI This dosing regimen was selected based on the totality of available clinical and nonclinical data and with careful consideration of the overall benefit-risk profile. Predicted plasma exposures of GS-441524 following this adult dosing regimen were used as the target exposure level for selecting pediatric ODV doses.

The developed PopPK model was used to select ODV doses for pediatric participants who will be enrolled in Cohort 1 Part A of this Phase 2 study (GS-US-685-6883). Upon availability of PK and safety data from a subset of participants in Cohort 1, the PopPK model will be updated to confirm ODV doses to be administered in Cohort 1 Part B and Cohort 2 and allow enrollment of neonate participants in this study (Section 3.1).

### 1.5. Benefit-Risk Assessment for the Study

Participants in this study will receive either ODV or placebo. Conducting a Phase 2 study to investigate the safety, tolerability, PK, and efficacy of ODV for the treatment of RSV is a measured approach that will provide data in the development of ODV as an oral treatment option for patients with RSV.

Moreover, ODV was found to be safe and well tolerated in participants evaluated in the COVID-19 program.

Obeldesivir has the potential benefit to be the first oral RSV treatment for children.

Potential risks of a participant's study involvement include unknown AEs, general risks associated with laboratory blood draws, and the associated pain and discomfort of phlebotomy.

Strategies to mitigate these risks include close monitoring of participants' clinical statuses, laboratory values, and AEs. Parameters for discontinuation of the study drug due to AEs will be clearly defined and closely followed.

An unanticipated event such as a disaster or public health emergency may pose additional risks to study drug availability, the study visit schedule, and adherence to protocol-specified safety monitoring or laboratory assessments (Section 7.7).

Considering the above, the benefit-risk balance for this study is considered positive.

## 2. OBJECTIVES AND ENDPOINTS

Primary Objectives	Primary Endpoints

 
To evaluate the safety and tolerability of ODV in pediatric participants with RSV infection
 
	
 
Proportion of participants experiencing treatment-emergent adverse events (TEAEs) by Day 28
 
Proportion of participants experiencing Grade 3 or 4 treatment-emergent laboratory abnormalities (TELAs) by Day 28
 

 
To evaluate the efficacy of ODV on duration of time until alleviation of targeted RSV symptoms in pediatric participants with RSV infection
 
	
 
Time to alleviation of targeted RSV symptoms by Day 28
 

Secondary Objectives	Secondary Endpoints

 
To evaluate the plasma PK of ODV in pediatric participants with RSV infection
 
	
 
PK parameters (<math>AUC_{tau}</math>, <math>C_{max}</math>, and <math>C_{trough}</math>) for ODV metabolite, GS-441524
 

 
To evaluate the antiviral activity of ODV on RSV nasal swab viral load in pediatric participants with RSV infection
 
	
 
Change from baseline in RSV nasal swab viral load at Day 5
 

 
To evaluate the efficacy of ODV on duration of time until sustained alleviation of targeted RSV symptoms in pediatric participants with RSV infection
 
	
 
Time to sustained alleviation of targeted RSV symptoms by Day 28
 

 
To evaluate the efficacy of ODV on duration of time until resolution of targeted RSV symptoms in pediatric participants with RSV infection
 
	
 
Time to resolution of targeted RSV symptoms by Day 28
 

 
To evaluate acceptability and palatability of ODV in pediatric participants with RSV infection
 
	
 
Assessment of palatability and acceptability scores of the age-specific formulation as assessed by caregiver at Days 1 and 5
 

Exploratory Objectives	Exploratory Endpoints

 
To evaluate the efficacy of ODV on duration of time until alleviation of targeted RSV symptoms, CCI [REDACTED], in pediatric participants with RSV infection
 
	
 
Time to alleviation of targeted RSV symptoms by Day 28, CCI [REDACTED]
 

 
To evaluate the efficacy of ODV on duration of time until sustained alleviation of targeted RSV symptoms, CCI [REDACTED], in pediatric participants with RSV infection
 
	
 
Time to sustained alleviation of targeted RSV symptoms by Day 28, CCI [REDACTED]
 

 
To evaluate the efficacy of ODV on duration of time until resolution of symptoms CCI [REDACTED], in pediatric participants with RSV infection
 
	
 
Time to resolution of targeted RSV symptoms by Day 28, CCI [REDACTED]
 

 
To evaluate the efficacy of ODV on severity of RSV symptoms in pediatric participants with RSV infection
 
	

 

 
 
Proportion of participants with RSV symptom alleviation per Health Care Professional Global Impression of Severity (HCPGI-S) scale at Days 1, 3, 5, and 10
 
Proportion of participants with RSV symptom alleviation per Caregiver Global Impression of Severity (CGI-S) scale at Days 1, 3, 5, 10, and 28
 
Proportion of participants with RSV symptom alleviation per Caregiver Global Impression of Change (CGI-C) scale by Days 3, 5, 10, and 28
 

 
To evaluate the impact of ODV on child health utility using the EuroQol-5 Dimension–child specific (3 levels) (EQ-5D-Y-3L; including visual analogue scale [VAS]) to be completed by the caregiver for the pediatric participant (proxy reported)
 
	
 
Change from baseline in index scores at Days 5, 10, and 28
 
Change from baseline in the VAS at Days 5, 10, and 28
 


 
To evaluate the impact of ODV on caregiver health utility using the EuroQol (5 dimensions, 5 levels) (EQ-5D-5L; including VAS) to be completed by the caregiver
 
	
 
Change from baseline in index scores for the caregiver at Days 5, 10, and 28
 
Change from baseline in the VAS for the caregiver at Days 5, 10, and 28
 

 
To evaluate the impact of ODV on caregiver burden using the Work Productivity and Activity Impairment (WPAI)-RSV questionnaire
 
	
 
Change from previous visit in absenteeism/presenteeism in work/education/volunteering at Days 10 and 28
 

 
To evaluate the antiviral activity of ODV on RSV nasal swab throughout the study period in pediatric participants with RSV infection
 
	
 
Proportion of participants with negative RSV nasal swab viral load and infectious viral titer at Days 1, 3, 5, and 10, as applicable
 
Change from baseline in RSV nasal swab viral load at Days 3 and 10, as applicable
 
Change from baseline in RSV nasal swab infectious viral titer at Days 3, 5, and 10, as applicable
 

 
To evaluate the emergence of viral resistance to ODV in pediatric participants with RSV infection
 
	
 
Emergence of viral resistance to ODV
 

 
To evaluate the efficacy of ODV in treating RSV in pediatric participants with respiratory coinfection
 
	
 
Symptom duration and virologic response in pediatric participants with respiratory coinfections
 

 
To evaluate the efficacy of ODV on duration of time until occurrence of RSV-related MAVsa, hospitalizationb, or death as assessed by the investigator in pediatric participants with RSV infection
 
	
 
Time to RSV-related MAVs, RSV-related hospitalization, or RSV-related death by Day 28
 


 
To evaluate the efficacy of ODV on duration of time until occurrence of MAVsa, hospitalizationb,
 
	
 
Time to all-cause MAVs, all-cause hospitalization, or all-cause death by Day 28
 

or death from any cause in pediatric participants with RSV infection	

a. MAV is defined as a medical visit attended in person by the participant and a health care professional, including primary pediatrician, urgent care visit, and emergency department visit.
 
b. Hospitalization is defined as observation at an emergency department or hospital admission for > 24 hours.
	

### 3. STUDY DESIGN

#### 3.1. Study Design Overview

This is a Phase 2, randomized, multicenter, double-blind, placebo-controlled study comparing the safety, tolerability, PK, and efficacy of ODV with placebo for the treatment of RSV infection in participants from birth to < 5 years of age with and without risk factors for severe RSV disease.

At least 130 nonhospitalized participants are planned to be randomized for this study across the following cohorts:

- Cohort 1 (approximately 106 participants): children and infants with weight at screening  $\geq 3$  kg to < 40 kg (Part A) and  $\geq 1.5$  kg to < 3 kg (Part B)
  - Children born at term (ie,  $\geq 37$  weeks gestational age [GA]) and  $\geq 28$  days to < 2 years chronological age
  - Preterm children (ie, < 37 weeks GA) with postmenstrual age (PMA)  $\geq 44$  weeks to < 2 years chronological age
  - Children  $\geq 2$  to < 5 years chronological age
- Cohort 2 (N  $\geq 24$ ): neonates with screening weight  $\geq 1.5$  kg to < 6 kg
  - Born at term (ie,  $\geq 37$  weeks GA) and < 28 days chronological age
  - Born preterm (ie, < 37 weeks GA) and PMA < 44 weeks

This study will initially enroll participants in Cohort 1 Part A. Enrollment in Cohort 2 and Cohort 1 Part B will be initiated following a review of safety and available PK data by a Safety Review Team (SRT) and a review of safety data by an independent data monitoring committee (DMC) after approximately 24 participants from Cohort 1 Part A have completed at least Day 5 assessments or prematurely discontinued the study. All cohorts will then continue to enroll participants in parallel. It is noteworthy that there will be no enrollment pause in Cohort 1 Part A during SRT/DMC reviews.

As ODV doses are defined based on weight groups, participants will be divided into different weight groups within each cohort. Within each cohort/weight group, enrolled participants will be randomized in a 2:1 ratio to receive ODV:placebo for CCI. Within each cohort, the dose administered to a participant will be based on their weight at baseline. The weight group categorizations for both cohorts are outlined in Section 5.4.

Gilead Sciences (Gilead) may close, delay, or suspend enrollment for any cohort or weight group at any time. Thus, not all cohorts or weight groups may be open for enrollment during the study.

### **3.1.1. Dose Selection/Modification for Cohorts**

The first SRT will confirm the ODV doses being used in Cohort 1 Part A after review of safety and available PK data from approximately 24 participants from Cohort 1 Part A who have completed at least Day 5 assessments or prematurely discontinued from the study. In addition, the first SRT will also confirm the ODV doses to be evaluated in Cohort 2 and Cohort 1 Part B.

The second SRT will confirm the ODV doses being used in Cohort 2 (and Cohort 1 Part B, if data are available) after review of safety and available PK data from approximately 12 participants from Cohort 2 who have completed at least Day 5 assessments or prematurely discontinued from the study.

The composition and summary of the SRT is provided in Appendix [11.3.1](#).

### **3.2. Duration of Intervention**

CCI

#### **3.2.1. Poststudy Care**

The long-term care of the participant will remain the responsibility of their primary treating physician.

### **3.3. Protocol-Specific Discontinuation Criteria**

#### **3.3.1. Criteria for Early Discontinuation for the Individual Participant**

##### **3.3.1.1. Criteria for Early Discontinuation From Study Intervention**

Study intervention will be discontinued in the following instances:

- Any serious adverse event (SAE) suspected to be related to study drug.
- Any Grade 3 or higher AE suspected to be related to study drug.
- An AE or worsening of clinical condition requiring clinical intervention, that would, in the judgment of the investigator, affect assessments of clinical status to a significant degree.
- Unacceptable toxicity, as defined in Section [7.7](#), or toxicity that, in the judgment of the investigator, compromises the ability to continue study-specific procedures or is considered not to be in the participant's best interest.
- Caregiver request to discontinue for any reason (Section [3.3.1.1.1](#)).
- Participant noncompliance.

- Any Grade 3 or higher clinically significant laboratory abnormality (if confirmed by repeat testing) suspected to be related to study drug.
- Alanine aminotransferase (ALT)  $\geq 5 \times$  upper limit of normal (ULN).
- Participants  $\geq 1$  year of age who have a confirmed eGFR  $< 80$  mL/min/1.73 m^2 by bedside Schwartz formula.
- Participants  $< 1$  year of age who have a confirmed creatinine level above the ULN as defined by the local laboratory and appropriate for the GA and chronological age.

#### 3.3.1.1.1. Partial Withdrawal

Participants/caregivers may decide to partially withdraw from the study (eg, discontinue from study intervention and/or procedures but agree to continue to be followed for study endpoints). Such partial withdrawals should be fully documented.

#### 3.3.1.2. Criteria for Early Discontinuation From the Study

The participant will be discontinued from the study early in the following instances:

- Caregiver request to discontinue for any reason (Section 3.3.1.1.1).
- Discontinuation of the study by sponsor.
- Participant noncompliance.
- Loss to follow-up (Section 6.4.1).
- Disaster or public health emergency (Appendix 11.4 provides information on risk assessment and mitigation that may allow continued participation.)
- Withdrawal of consent/assent.
- Death.

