### 6.4. Procedures for Early Discontinuation From Study Intervention or From the Study

If a participant discontinues study intervention early (eg, as a result of an AE), every attempt should be made to keep the participant in the study and continue to perform study-related follow-up and procedures (Section [3.3](#)). If this is not possible or acceptable to the participant or investigator, the participant may be partially withdrawn from the study (Section [3.3.1.1.1](#)) to enable collection of study endpoint information or completely withdrawn from the study.

If a participant discontinues from the study early, the participant will be asked to return to the investigational site within 2 days to attend an ET visit for assessment and procedures specified in [Table 1](#).

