**Table 6. Primary Estimand for Primary Efficacy Endpoint**

Attribute	Details
Target population	Study population as defined by protocol eligibility criteria
Treatment condition(s)	ODV and placebo, regardless of treatment discontinuation/modification, RSV-related hospitalization, or RSV-related MAVs
Variable	Time (days) to alleviation of targeted RSV symptoms by Day 28 in the absence of rescue medication and all-cause death
Handling of ICEs	
The following scenarios if they occur prior to alleviation of targeted RSV symptoms by Day 28 will be considered:
 
 
• Treatment discontinuation/modification: treatment policy (included as part of the treatment condition(s) attribute)
 
• Use of rescue medication: composite strategy (included as part of the variable attribute). Note: details on the applicable rescue medications will be provided in the SAP
 
• All-cause death: composite strategy (included as part of the variable attribute)
 
• RSV-related hospitalization: treatment policy (included as part of the treatment condition(s) attribute)
 
• RSV-related MAVs: treatment policy (included as part of the treatment condition(s) attribute)
 

Population-level summary	Difference in median variable (as defined in the variable attribute) between ODV and placebo

ICE = intercurrent events; MAV = medically attended visit; ODV = obeldesivir; RSV = respiratory syncytial virus; SAP = statistical analysis plan

The estimate of the primary estimand is the difference in median time (days) to alleviation of targeted RSV symptoms by Day 28 in the absence of rescue medication and all-cause death between ODV and placebo as defined by protocol eligibility criteria. This will be estimated regardless of treatment discontinuation/modification, RSV-related hospitalization, or RSV-related MAVs (ie, treatment policy).

The time to alleviation of targeted RSV symptoms by Day 28 is calculated as the symptom alleviation date minus the first dose date. In case, prior to data cutoff a participant:

- Completes the study without alleviation of targeted RSV symptoms
- Prematurely discontinues from the study prior to alleviation of targeted RSV symptoms (due to AE, lack of efficacy, investigator's discretion, noncompliance with study drug, protocol violation, participant decision, lost to follow-up)

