6.1.2. Primary Analysis of the Primary Efficacy Endpoint

The primary estimand for the primary efficacy endpoint is outlined in the following table.

Table 6-1. Primary Estimand for Primary Efficacy Endpoint

Attribute	Details
Target population	Study population as defined by protocol eligibility criteria
Treatment condition(s)	ODV and placebo, regardless of treatment discontinuation/modification, RSV-related hospitalization, or RSV-related MAVs
Variable	Time (days) to alleviation of targeted RSV symptoms by Day 28 in the absence of rescue medication and all-cause death
Handling of ICEs	The following scenarios if they occur prior to alleviation of targeted RSV symptoms by Day 28 will be considered: 
• Treatment discontinuation/modification: treatment policy (included as part of the treatment condition(s) attribute)• Use of rescue medication: composite strategy (included as part of the variable attribute). Note: details on the rescue medications are presented in Appendix 4.• All-cause death: composite strategy (included as part of the variable attribute)• RSV-related hospitalization: treatment policy (included as part of the treatment condition(s) attribute)• RSV-related MAVs: treatment policy (included as part of the treatment condition(s) attribute)
Population-level summary	Difference in median variable (as defined in the variable attribute) between ODV and placebo

ICE = intercurrent events; MAV = medically attended visit; ODV = obeldesivir; RSV = respiratory syncytial virus

For participants with targeted RSV symptom alleviation by Day 28 (ie, event), the time to alleviation of targeted RSV symptoms by Day 28 is calculated as the symptom alleviation date/time minus the first dose date/time (expressed as days with 8 decimal places). In the analysis output, 1 decimal place in days will be used for display purposes.

In case, a participant:

- Completes the study without alleviation of targeted RSV symptoms (ie, censored)
- Prematurely discontinues from the study prior to alleviation of targeted RSV symptoms (due to AE, lack of efficacy, investigator's discretion, noncompliance with study drug, protocol violation, participant decision, lost to follow-up) (ie, censored)

The time to alleviation of targeted RSV symptoms will be calculated as the last date and time on which the symptom alleviation is assessed or 23:59:00 on Day 27, whichever occurs first, minus the first dose date and time.

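### Protocol 3.3.1.2 makes undefined noncompliance a mandatory reason to leave the study, against the treatment-policy estimand and the protocol's own retention text

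*Protocol*

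**What the plan says.** Protocol 3.3.1.2 opens with "The participant will be discontinued from the study early in the following instances" and includes the bullet "Participant noncompliance". It gives no definition, threshold or room for judgement. The same bullet stands in Section 3.3.1.1 under "Study intervention will be discontinued in the following instances", so one trigger governs both study drug and study participation.

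Protocol 8.5.1, below Table 6, describes premature study discontinuation as "due to AE, lack of efficacy, investigator's discretion, noncompliance with study drug, protocol violation, participant decision, lost to follow-up". SAP 6.1.2 repeats the reasons ("lack of efficacy, investigator's discretion, noncompliance with study drug, protocol violation, participant decision, lost to follow-up") and marks these participants as censored. SAP 6.2.1.1 and 6.2.1.2 do the same for sustained alleviation and resolution.

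The treatment condition in the primary estimand (Protocol Table 6, SAP Table 6-1) is "ODV and placebo, regardless of treatment discontinuation/modification, RSV-related hospitalization, or RSV-related MAVs". SAP 6.1.2 adds that treatment discontinuation or modification is to be ignored in the analysis. For children who stop drug early, Protocol 6.4 says "every attempt should be made to keep the participant in the study and continue to perform study-related follow-up and procedures".

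**The concern.** A treatment-policy strategy needs outcomes observed after treatment stops or changes. A child who stops drug for noncompliance under 3.3.1.1 has exactly the intercurrent event that the estimand intends to follow through. Under 3.3.1.2, the same trigger also takes that child out of the study. If a site applies the text as written, the caregiver diary, later swabs and scheduled adverse event contacts end, and time to alleviation is censored.

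The primary efficacy endpoint and the Day 28 safety proportions are both exposed. The loss need not be random. Refusal of doses may depend on how ill the child is or on taste, and palatability is itself a secondary endpoint that could differ between arms.

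**Working it through.** The documents give no noncompliance or dropout rate, effect size or event count, so there is no planned figure to reproduce. The check is mainly a comparison of text.

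**1. The passages side by side**

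| Place | Effect on a child judged noncompliant with dosing |
|---|---|
| Protocol 3.3.1.1 | Study drug stops |
| Protocol 3.3.1.2 | Leaves the study (mandatory) |
| Protocol 8.5.1; SAP 6.1.2, 6.2.1 | Named as a study-exit reason; censored in the SAP |
| Protocol Table 6; SAP Table 6-1 and 6.1.2 | Treatment policy: stopping or changing drug does not end observation |
| Protocol 6.4 | Kept in follow-up after stopping drug |
| Protocol 5.1.4 (on unblinding) | All participants followed to completion unless consent is withdrawn |
| Protocol 3.4.2 | Early end of study only through death, withdrawn consent, loss to follow-up or sponsor termination |
| Protocol 3.3.1.1.1 | Partial withdrawal is available, but as the participant's or caregiver's choice |

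Rows 2 and 3 cannot be reconciled with rows 4 to 7. Row 8 does not override row 2.

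**2. Diary time lost.** Dosing covers Days 1 to 5 (Day 6 if only one dose was taken on Day 1). The diary runs to Day 28 or early termination (Protocol Table 1). Withdrawal at Day 5 loses up to 28 − 5 = 23 days. If the diary continues to an early termination visit two days later (Protocol 6.4), the loss is 28 − 7 = 21 days. A child whose symptoms had already been alleviated loses nothing on the primary endpoint.

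**3. Safety.** Protocol 7.3.2 collects adverse events to 30 days after the last dose and makes no exception for noncompliance. A child who has left the study no longer has the scheduled contacts through which events are found. The child stays in the Safety Analysis Set with shorter observation.

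**4. Scale for one arm, on assumed inputs.** Assume exponential time to alleviation with a 10-day median in compliant children, so λ = ln 2 / 10 = 0.0693 per day. A fraction f = 20% is withdrawn at Day 5, with hazard rλ.

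- Median with full follow-up solves 0.8·exp(−λt) + 0.2·exp(−rλt) = 0.5.
- Kaplan-Meier median with censoring at Day 5 is 5 + ln(S(5)/0.5)/λ, where S(5) = 0.8·exp(−5λ) + 0.2·exp(−5rλ).

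| r | S(5) | Full follow-up | With censoring | Error (days) |
|---|---|---|---|---|
| 0.5 | 0.566 + 0.168 = 0.734 | 11.3 | 5 + 0.384/0.0693 = 10.5 | about −0.8 |
| 1 | 0.707 | 10.0 | 10.0 | 0 |
| 2 | 0.566 + 0.100 = 0.666 | 8.6 | 5 + 0.286/0.0693 = 9.1 | about +0.5 |

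A simulation over medians of 6, 8 and 10 days, f of 5%, 10% and 20%, and the same r gave no larger errors. About 2% to 11% of participants had an alleviation that went unobserved. At the mild end (6 days, 5%, r = 0.5) the medians were 6.19 and 6.15 days.

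**5. What is now planned.** SAP 6.3 confines efficacy to descriptive summaries. SAP 6.1.2 summarises times separately for events and censored participants, so a withdrawn child without prior alleviation appears only among the censored.

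**The case against.** Noncompliance is undefined. It could mean missed doses in 3.3.1.1 and missed study procedures in 3.3.1.2. The list of reasons in Protocol 8.5.1 and SAP 6.1.2 also names adverse events, lack of efficacy, investigator's discretion and protocol violation, none of which is a bullet in 3.3.1.2. It can therefore be read as a generic disposition list that says how to handle a child who has left, without telling a site to remove anyone. Sections 3.4.2, 5.1.4 and 6.4 all point towards retention.

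Part of this stands. A reader might infer that any child who misses a dose is removed. The documents do not say so: Protocol 7.1.4 places a missed dose under medication error, and only children judged noncompliant come under the rule. A reader might also infer that these children drop out of the analysis. They do not: data up to withdrawal and an early termination visit are kept, and being withdrawn does not remove a child from the FAPS or the Safety Analysis Set.

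The contradiction remains. The rule in 3.3.1.2 is mandatory as worded, no passage limits it to procedures, and both documents expect dosing noncompliance to be a recorded reason for study exit. The retention passages show that the text disagrees with itself; they do not exempt noncompliance from the rule.

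**Conclusion.** The concern holds as an internal contradiction with a practical consequence. Followed as written, 3.3.1.2 truncates follow-up that the primary estimand requires. For a child withdrawn at Day 5 the loss is up to 23 of 28 diary days plus part of the safety follow-up.

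The size and direction of any bias are unknown. A reader might infer a bias in favour of ODV, on the reasoning that refusal is commoner on active drug and that refusers recover more slowly. Suppose 5–15% noncompliance on ODV and 2–5% on placebo, with 50% of withdrawn and 70% of other children alleviated by a given day. The true ODV figure is then 0.95 × 0.70 + 0.05 × 0.50 = 69% down to 0.85 × 0.70 + 0.15 × 0.50 = 67%, against 70% observed, an error of 1 to 3 points. Placebo has an error too: 0.98 × 0.70 + 0.02 × 0.50 = 69.6% down to 0.95 × 0.70 + 0.05 × 0.50 = 69%, or 0.4 to 1 point. Pairing low with low and high with high, the net is 0.6 to 2 points. Every input is assumed, the sign reverses if withdrawn children recover faster, and the estimand is a difference in medians. The documents do not support a directional claim.

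The multiple-imputation sensitivity analysis in Protocol 8.5.1 is optional, assumes missing at random, and does not appear in the readable SAP text. Early termination and the descriptive SAP reduce the practical impact without resolving the contradiction.

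**What to change.** - **Protocol 3.3.1.2:** remove noncompliance with study drug as a ground for leaving the study. If a ground for noncompliance with study procedures is wanted, define it. Leave 3.3.1.1 as it is.
- **Retention:** state that children judged noncompliant with dosing stay in scheduled follow-up (diary, swabs, adverse event contacts) to Day 28 unless consent is withdrawn, so that 3.3.1.2, 3.4.2, 5.1.4, 6.4 and 8.5.1 agree.
- **SAP 6.1.2 and 6.2.1:** keep the censoring rule for any child who does leave, whatever the recorded reason. Deleting the noncompliance phrase there would recover no data and would leave such exits without a stated rule.
- **This trial:** an amendment cannot recover follow-up already lost. The clinical study report should give study exits for noncompliance by arm and note the departure from treatment policy. SAP 4.1 already tabulates reasons for study discontinuation by treatment group.
- **Reuse:** carry the correction into any later protocol that takes over this text.

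The cost is a few lines of protocol text and a sentence in the report. No new visits are needed, because those concerned are already in the schedule.
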